## 3.2. Primary Hypothesis #2: Impact of Blood Pressure Treatment on Poor Fetal Growth (i.e. SGA<10th percentile based on birth weight)

 $H_0$ : There will be no difference in the rate of poor fetal growth in CHAP participants treated in the Low BP group therapy compared to participants in the Standard BP group.

- **3.2.1. Poor Fetal Growth Outcome:** We will examine small for gestational age (SGA) infants identified as <10th percentile based on birth weight at the delivery gestational age. SGA has not been included in the composite, because the concerns that therapy may be a cause (impaired placental blood flow) of SGA, it is assessed separately as the primary safety outcome to evaluate harms. *The two primary hypotheses provide clear endpoints for benefit versus harm. Based on our preliminary data, however, BP control may be associated with a reduction in risk of SGA*. A national standard weight curve presently planned to be Alexander's, but may be modified prior to data closure with another acceptable customized curve used to identify SGA infants at the time of analysis. We will also, secondarily, examine extreme SGA <5th and <3rd percentiles.
- **3.2.2. Analysis Plan:** The  $\chi^2$  test of association will be used to evaluate whether the rate of the SGA differs between the two blood pressure management approaches. The primary analysis will follow the

analysis plan for the composite primary outcome. Specifically, for cases where the primary composite outcome is undetermined (for example, dropout prior to delivery), the primary analysis will utilize multiple imputation based on the characteristics within treatment group that are predictive of the SGA outcome. Logistic regression models will be fit within treatment group using baseline characteristics predictive of the SGA outcome and this group-specific model will be used to provide the imputed outcome values. Up to 5 replicates will be considered. All individuals will be analyzed as randomized to the two treatment groups, regardless of whether they adhered to their assigned treatment. Sensitivity analyses will follow the primary outcome analysis plan described above. Relative rates (RR) and 95% confidence intervals (CIs) will be computed and presented, as well as individual group rates and 95% CIs. In the event of imbalanced patient characteristics in the two groups, multivariable modeling will be performed as described in the previous section.

**3.2.3. Power for other outcomes:** The sample size of 2404 provides adequate power to examine SGA and key components of the primary outcome separately. The corresponding power for each outcome considering conservative estimates of baseline incidence and effect sizes given a 2-sided alpha of 0.05 are shown in Table 3.

Table 3: Power – SGA and Secondary Outcomes

Outcome	Incidence	Effect size %	Power
SGA	10-14%	35-40	≥85%
Preeclampsia	20%	25	>85%
Cardiovascular	4-6%	50	80-90%
Preterm birth	20%	25	>85%
Perinatal death	4-6%	50	80-90%

The baseline risks of SGA, preeclampsia, preterm birth and perinatal death are likely to be higher considering the literature reviewed and our preliminary data, thus power may actually be higher. The incidence of the rare maternal cardiovascular outcome is not well characterized. This study will provide a more precise estimate and will consider any new heart failure, stroke or encephalopathy, and MI/angina as cardiovascular outcomes.

**3.3 Interim Monitoring**: The study investigators, in conjunction with the study DSMB and NHLBI, propose 1 interim analysis for the CHAP trial. In order to maintain maximum power for the final analysis, and to simultaneously protect the overall type I error of the study, we propose that alpha levels at the interim analysis be selected using a Lan-DeMets alpha spending function that follows O'Brien-Fleming boundaries.

The formal interim analysis will be conducted when 50% (n=1202) of the total sample size (n=2404) has completed the study. The first 1202 consecutive women enrolled in the study will be reviewed for primary outcomes following their last study visits. All suspected primary outcomes included in the composite primary outcome will undergo review for adjudication. The interim analysis will focus on the analysis of these adjudicated outcomes. Group totals and rates will be presented in a masked fashion (using A and B labels rather than actual treatment assignment labels), where only the study statistician will know the true identity of A and B. The masked labels will be removed and true group assignments revealed only upon request by the DSMB.

The 1202 for this interim analysis will include the 800 that were considered for the SSR. In order to maintain maximum power for the final analysis, and to simultaneously protect the overall type I error of the study we will implement a Lan-DeMets alpha spending function that follows O'Brien-Fleming boundaries. The timing of this evaluation is chosen such that it will allow sufficient time for adding

additional sites; complete regulatory requirements and allow them to actively participate in the trial with enrollment of the needed number of additional patients.

To summarize this approach, suppose that  $X_i^2$  (i=1,2) represents the usual chi-square test statistic for the primary outcome at the ith look (note that i =2 corresponds to the final look), then at the interim look:

Reject H0 if  $\chi_1^2 > 9$  (i.e. p < 0.0027), and stop study for efficacy; otherwise, continue.

And at the final look:

Reject H0 if 
$$\chi_i^2 > 3.87$$
 (i.e. p < 0.0492).

We do not propose a formal stopping rule for safety, but note the DSMB will continuously monitor for safety.

The interim analysis will include statistical significance testing only for the primary composite outcome, components of the primary outcome, and SGA  $<10^{th}$  percentile.

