#### 2. Systematic reviews:

i. A single systematic review (7 trials in 623 women) focused solely on antihypertensive therapy in pregnant women with CHTN (excluding gestational hypertension or preeclampsia) at baseline. The results are depicted in Figure 1. The observed reduction in severe hypertension in treated patients was not accompanied by significant reductions in key adverse pregnancy outcomes. Results for indicated preterm birth, which is the specific type of preterm birth associated with CHTN, were not available.

ii. A Cochrane review included 4282 women with CHTN as well as gestational HTN or preeclampsia who were enrolled in 46 small trials of antihypertensive therapy. Overall, antihypertensive treatment with any drug versus no treatment/placebo lowered the incidence of severe HTN (RR 0.5; 95% CI 0.41-0.61). There were no significant differences between treatment groups in preeclampsia (0.97; 0.83-1.13), eclampsia (0.34; 0.01-8.15), perinatal death (0.73; 0.50-1.08), PTB (0.98; 0.85-1.13), SGA (1.04; 0.84-1.27), abruption (1.83; 0.77-4.37) or maternal death. There were reductions in fetal loss (0.39; 0.17 - 0.93) and in neonatal respiratory distress syndrome (0.28; 0.12- 0.63) with treatment.

Methyldopa alone versus no treatment was associated with a lower incidence of fetal or neonatal death (0.35; 0.13 - 0.94). Analyses restricted to women with CHTN yielded similar results but corresponding data for fetal loss and respiratory distress were not available. Use of a placebo in the control group did not influence results. Considering the limited size and flaws of the individual trials (particularly combining patients with disparate types of hypertension), the authors concluded that:

- i. it remains unclear whether anti-hypertensive therapy for mild CHTN in pregnancy is worthwhile; and
- ii. larger trials are needed to provide reliable data on the benefits and harms of treatment for mild CHTN in pregnancy. Importantly, women with CHTN at baseline are distinctly different from those with gestational hypertension or preeclampsia, and perhaps more likely to benefit or suffer harm from therapy, and therefore should be studied separately.

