Sensitivity analyses will be performed as described above. Supplementary analyses will consider best-case and worst-case scenarios. Specifically, we will consider all missing outcomes in the Lower group to be non-outcomes and those in the Standard group to be outcomes. The reverse will also be considered, where all missing outcomes in the Lower group will be outcomes and those in the Standard group will be non-outcomes. Consistency of effect estimates and statistical significance will be examined across all analytic approaches.

**3.1.3. Original Sample Size for Primary Outcome:** We used data from the MFMU Network's High Risk Aspirin study (enrollment into the CHTN group was based on pragmatic clinic BPs) to estimate the frequency of the composite outcome components among 763 women with mild CHTN at baseline as follows: Fetal or neonatal death = 6.16%; severe preeclampsia (severe hypertension and proteinuria, eclampsia, preeclampsia with thrombocytopenia, creatinine>1.4, elevated liver enzymes) =0.66%; abruption =1.46%; indicated PTB <35 weeks =12.32%. The frequency of the primary composite outcome was assessed as 16%. Assuming a 2-sided alpha of 0.05 and conservative baseline incidence of 16% (since this is regardless of BP lowering therapy, and we expect the incidence to be higher in those not receiving therapy) the unadjusted sample sizes/arm needed to detect a 20-30% reduction in the primary outcome with 85-90% power are presented in Table 1. These unadjusted estimates do not take into account drop-ins and drop- outs or the interim look we propose. We assume: the 10% of the control group that will require treatment for severe hypertension are already well-accounted for in our baseline rate of 16% estimated from usual care; we assume there will be up to an additional 10% rate of protocol

violations (treatment in the Standard BP group without meeting criteria for severe hypertension) and that nonadherence in the Lower BP group is 10%. The adjusted outcome rates for 25% reduction are: 15.6% and 12.4%, respectively and the adjusted sample sizes/arm accounting additionally for 8% loss-to-follow up are presented in Table 1.

Table 1: Estimated sample size/arm (30%, 25% and 20% Reductions) under original plan

	30% REDUCTION		25% REDUCTION		20% REDUCTION	
Power	Unadjusted	Adjuste d	Unadjusted	Adjusted	Unadjusted	Adjusted
90%	1075	1829	1587	2696	2539	4314
85%	919	1561	1356	2305	2170	3687

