Based on studies published following the approval of the CHAP trial, it was hypothesized that the overall event rate for the CHAP study was underestimated along with the expected reduction in the primary outcome. In addition, participant accrual during the trial was slower than anticipated, arising from the underestimation of the yield from screening to randomization. A revised sample size (n=2404) was proposed that incorporated a larger 33% reduction in the primary outcome and thus reflected a more feasibly attainable target sample size. The total sample size of 2404 reflects a 33% reduction in the primary outcome (from a baseline rate of 16%), 10% noncompliance, 10% crossover, and 85% power. As seen in Table 2 below, the necessary sample size per group is 1142 when incorporating these criteria; accounting for 5% attrition inflates the sample size per group to 1202 (n=2404 total).

Table 2: Estimated sample size/arm (33%, 30nd 25% Reductions) under revised plan as of January 2019

	33% REDUCTION		30% REDUCTION		25% REDUCTION	
Power	Unadjusted	Adjusted	Unadjusted	Adjusted	Unadjusted	Adjusted
90%	868	1336	1075	1829	1587	2696
85%	748	1142	919	1561	1356	2305

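### SAP 3.2.3 claims adequate power for key components of the primary outcome, but Table 3 supports this only for perinatal death, and only at a 50% reduction

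*Combined protocol and SAP*

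**What the plan says.** SAP 3.2.3 makes the claim: "The sample size of 2404 provides adequate power to examine SGA and key components of the primary outcome separately". The supporting sentence says that the "effect sizes given a 2-sided alpha of 0.05 are shown in Table 3". Table 3 gives power for SGA (10–14%, 35–40% reduction), preeclampsia (20%, 25%), cardiovascular outcome (4–6%, 50%), preterm birth (20%, 25%) and perinatal death (4–6%, 50%).

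SAP 3.1.1 defines four components: fetal or neonatal death, superimposed preeclampsia with severe features, placental abruption, and indicated preterm birth before 35 weeks. SAP 3.1.3 takes their rates from an earlier aspirin trial: death 6.16%, severe preeclampsia 0.66%, and "abruption =1.46%; indicated PTB <35 weeks =12.32" (the last figure also a percentage).

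The revised design in SAP 3.1.4 assumes a 33% reduction from 16%, with "10% noncompliance, 10% crossover, and 85% power". It needs 1142 per arm, or 1202 after allowing for 5% attrition. SAP 3.3 lists "components of the primary outcome, and SGA" below the 10th percentile among the outcomes tested for significance at the interim, and SAP 4.3 has the components presented with the primary results.

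**The concern.** The claim is in the plural and concerns components, yet the table behind it covers one. The preeclampsia row cannot stand in for severe preeclampsia, nor the preterm birth row for indicated birth before 35 weeks: SAP 4.3 lists preeclampsia of any severity and preterm birth before 37 weeks as separate outcomes. The row that does match assumes a 50% reduction, well above the 33% on which the trial is sized.

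The stake is interpretation. If the SAP has declared adequate power in advance, a non-significant result for death or abruption can be taken as evidence that treatment has no effect on it, when the trial may have had little chance of detecting one.

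**Working it through.** **Inputs.** Component rates: SAP 3.1.3. Effect (33%), noncompliance and crossover (10% each), 1142 and 1202 per arm: SAP 3.1.4. Two-sided alpha 0.05: SAP 3.2.3.

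**Formula.** Two proportions, pooled variance under the null, with p̄ = (p1 + p2)/2:

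power = Φ{ [|p1 − p2| − 1.96·√(2p̄(1 − p̄)/n)] / √([p1(1 − p1) + p2(1 − p2)]/n) }

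**Step 1: reproduce Table 3** (1202 per arm, no dilution; 1142 in brackets).
- SGA 10%, 35% reduction: 87.7% (86.0%). SGA 14%, 40%: 99.2% (98.9%). Stated: at least 85%.
- Preeclampsia and preterm birth 20%, 25%: 89.8% (88.2%). Stated: above 85%.
- Perinatal death and cardiovascular, 4% and 6%, 50%: 82.0% and 94.4% (80.0% and 93.3%). Stated: 80–90%.

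The table essentially reproduces, so it was built without dilution; only the 90% upper end is a little low.

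**Step 2: one component in full.** Death: p1 = 0.0616, p2 = 0.67 × 0.0616 = 0.0413, difference 0.02033, p̄ = 0.05144. Standard errors at n = 1202 are 0.00901 (null) and 0.00900 (alternative). Then (0.02033 − 1.96 × 0.00901)/0.00900 = 0.30, and Φ(0.30) gives 62%.

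**Step 3: dilution.** Control rate = 0.9p + 0.1p(1 − e); treated rate = 0.9p(1 − e) + 0.1p. For p = 16% and e = 25% this returns 15.6% and 12.4%, the adjusted rates in SAP 3.1.3. For e = 33% the multipliers on p are 0.967 and 0.703.

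**Step 4: all four components** (power, %).

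| Component (rate) | 33%, 1202/arm, undiluted | 33%, 1142/arm, diluted | 25%, 1202/arm, undiluted | 50%, 1202/arm, undiluted |
|---|---|---|---|---|
| Indicated preterm birth <35 weeks (12.32%) | 91 | 73 | 68 | >99 |
| Fetal or neonatal death (6.16%) | 62 | 42 | 39 | 95 |
| Abruption (1.46%) | 19 | 13 | 12–13 | 40–41 |
| Severe preeclampsia (0.66%) | 11 | 8–9 | 8 | 21 |

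Where two figures appear, the second also counts rejections in the wrong direction.

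At 33%, undiluted, the numbers per arm needed for 85% power are about 1002, 2119, 9314 and 20745, in the order of the table. Expected abruptions are 1202 × 0.0146 = 17.5 against 11.8.

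**Step 5: sensitivity to the rates.** For severe preeclampsia at a 33% reduction, 1202 per arm, undiluted, assumed rates of 3%, 5%, 10% and 15% give 34%, 52%, 83% and 96%. Diluted at 1142 per arm they give 23%, 35%, 63% and 82%. For abruption at 33%, undiluted, multiplying the rate by 1.5 gives 26% and doubling it gives 33%. Doubling the rate and assuming a 50% reduction together gives 69%.

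**The case against.** Several counter-arguments have force.

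- **The SAP says key components and does not name them.** Read narrowly, as death alone at the effect Table 3 states, the claim is supported: 95% at 6.16% and 50%. That stands. But the wording is plural, and an unnamed set cannot be checked.
- **The 33% effect belongs to the composite.** True, and which component passes depends on the effect chosen. With Table 3's own effects (death 50%, preterm birth 25%, preeclampsia 25%) carried over to the components, death has 95%, indicated preterm birth 68% and severe preeclampsia 8%. Abruption has no stated effect.
- **The 0.66% rate does not fit this trial's definition.** This stands. The source counted creatinine above 1.4 and laboratory criteria; protocol 4.7.1 uses creatinine of at least 1.2 and adds persistent symptoms and pulmonary edema. Protocol Table 2 gives severe preeclampsia rates that average about 3% overall ((478 × 1.9 + 221 × 5.9 + 60 × 1.7)/759) and 5% at 140/90 or above. SAP 3.1.4 also reports a higher overall event rate than expected, with the figures withheld. Power for this component is therefore unknown rather than shown to be 11%.
- **Risk ratios with confidence intervals are planned**, so an imprecise null would be visible. That limits the harm but does not make the power statement correct.

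Four stronger readings are tempting but not supported:

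- A reader might infer that a 50% reduction in death is the extreme of the cited evidence, because the systematic review in protocol 2.6.2.1 reports "perinatal death (0.73; 0.50-1.08". The same review gives 0.39 for fetal loss and, for methyldopa, 0.35 for fetal or neonatal death.
- A reader might infer that the SAP claims more than protocol 5.2, which speaks of key secondary outcomes. Protocol 4.7.2 lists the components among the major secondary outcomes, so that phrase can include them.
- A reader might infer that Table 3 is miscalculated. It is not (Step 1).
- A reader might fault component power at the interim. The SAP claims none there; its sentence concerns 2404 women.

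**Conclusion.** The component claim in SAP 3.2.3 goes beyond what Table 3 or the SAP's own inputs support. At the stated rates and a 33% reduction without dilution, one component of four exceeds 85% (indicated preterm birth, 91%), and death has 62%. With the plan's dilution none reaches 85%. Death is well powered only if the reduction is near 50%. Abruption is the clearest failure: at 1.46% it has 19% at the design effect and about 41% at most with a 50% reduction.

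It would be wrong to conclude that no component is powered, or to quote 11% for severe preeclampsia as established. These results rest on component rates from the earlier aspirin trial and on applying the composite's relative reduction to each component. The point concerns the scope of one sentence; the primary analysis, its power and the SGA power statement are unaffected.

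**What to change.** Keep the SGA power statement and the reference to Table 3, and restate the part on components, for example:

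> With 2404 women, power for SGA and for the other outcomes in Table 3 is adequate at the effect sizes shown there. Power for individual components of the primary outcome varies by component. It is low for abruption, and for fetal or neonatal death unless the reduction is near 50%. Components are reported with risk ratios and 95% confidence intervals, and a non-significant component result does not show absence of effect.

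Add a row to Table 3 for each component with its assumed rate, effect and power, using the Step 4 figures. Give severe preeclampsia as a range over assumed rates, and say whether the figures include dilution.

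The cost is a paragraph and a few table rows in the SAP. Sample size, data collection and planned tests stay as they are. The downside is that the stated power becomes less favourable.

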### 4. Additional Analyses

For the primary outcome, both intent-to-treat (as the primary) and a per-protocol approach will be used. The per-protocol population will be defined as those individual in the Lower BP (treatment) group who have >80% compliance and attendance at all scheduled visits. No adjustments will be made in the Standard Group since this provides our pragmatic control group. Secondary analyses will be examined accounting for the duration of therapy, prior antihypertensive therapy, race/ethnicity, pre-existing diabetes, GA at initiation of therapy and other covariates.

Pre-pregnancy and/or early pregnancy BMI will be evaluated for possible effects on all outcomes. Sensitivity analyses will be conducted to examine these possible effects. We will also evaluate potential interactions between BMI and treatment assignment. Subgroup analyses (by BMI class) will be explored where warranted. Similar interactions with other key patient characteristics will be examined.

Event free survival for the first occurrence of any of the primary outcome composite variables and will be calculated using Kaplan Meier estimates with testing via a log rank test. Student's t-test for comparisons of continuous outcomes (duration of hospital, NICU stay, etc.) will be conducted as well as regression analyses adjusting for pertinent covariates.

4.1 Secondary Aims/Hypotheses: Secondary outcomes will be compared using methods and approaches outlined above. The incidence of each of the 3 outcomes for this aim (perinatal death, composite neonatal morbidity, and composite of severe maternal morbidity) will be compared by completed weeks. To investigate the impact on the timing of delivery, longitudinal analysis of the full trial cohort with treatment arm as a key covariate, using completed gestational age (weeks 36-40) and their interaction as the independent variable will be implemented to assess the incidence of each of the 3 outcomes. The OR (95% CI) at each gestational age relative to 39 weeks will be computed and then adjusted for relevant covariate characteristics using logistic regression. Additional analyses will involve computing the adjusted OR and 95% CI for each outcome given delivery at a specific gestational age vs. at term. We will assess whether there is a gestational age beyond which waiting to deliver might be harmful.

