#### 5.1.1 Original Sample Size

We used data from the MFMU Network's High Risk Aspirin study (enrollment into the CHTN group was based on pragmatic clinic BPs) to estimate the frequency of the composite outcome components among 763 women with mild CHTN at baseline as follows: Fetal or neonatal death = 6.16%; severe preeclampsia (severe hypertension and proteinuria, eclampsia, preeclampsia with thrombocytopenia, creatinine>1.4, elevated liver enzymes) =0.66%; abruption =1.46%; indicated PTB <35 weeks =12.32%. The frequency of the primary composite outcome was 16%. Assuming a 2-sided alpha of 0.05 and conservative baseline incidence of 16% (since this is regardless of BP lowering therapy, and we expect the incidence to be higher in those not receiving therapy) the unadjusted sample sizes/arm needed to detect a 20-30% reduction in the primary outcome with 85-90% power are presented in Table 5. These unadjusted estimates do not take into account drop-ins and drop-outs or the interim look we propose. We assume: the 10% of the control group that will require treatment for severe hypertension are already well-accounted for in our baseline rate of 16% estimated from usual care; that in addition there will be up to a 10% rate of protocol violations (treatment in the control group without meeting criteria for severe hypertension) and that nonadherence in the treatment arm is 10%. The adjusted outcome rates for 25% reduction are: 15.6% and 12.4%, and the revised adjusted sample sizes/arm accounting additionally for 8% loss-to-follow up are presented in Table 5.

Table 5: Estimated sample size/arm (30%, 25% and 20% Reductions) under original plan

	30% REDUCTION		25% REDUCTION		20% REDUCTION	
Power	Unadjusted	Adjusted	Unadjusted	Adjusted	Unadjusted	Adjusted
90%	1075	1829	1587	2696	2539	4314
85%	919	1561	1356	2305	2170	3687

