## 5.3 Analysis Plan

A detailed analysis plan is described in a separate SAP. This section summarizes the main considerations for data analysis.

The key analyses for this study are the comparisons reflected by the primary and secondary aims; both intent-to-treat (as the primary) and a per-protocol approach will be used.

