Risk ratios (RR) and 95% confidence intervals (CIs) will be computed and presented, as well as individual group rates and 95% CIs. Standard comparison of the covariate characteristics at baseline between study groups will be undertaken (Section 2) to assess the randomization balance on measured covariates. Tests of significance will be two-sided and evaluated at the 0.05 level of significance. Since the sample size for CHAP is large, it is unlikely that "important" covariates (such as race, BMI or age) will be imbalanced through the randomization process. However, in the unlikely event that this occurs, adjustment for covariates will be made by modeling the log-odds of the outcome using multivariable logistic regression including terms indicating group membership, site and each of the imbalanced covariates. In other words, the log-odds of the primary outcome for any individual will be modeled using the following form:

$$\ln\left(\frac{P(outcome)}{1-P(outcome)}\right) = \beta_0 + \beta_1 x_1 + \sum \beta_j z_j.$$

Above,  $x_l = 1$  if the patient is in the Lower BP group (treatment) and equals 0 if the patient is in the Standard BP group (no-treatment). The set of  $z_j$ 's consists of all covariates in the model including site. Hence, under this model, the term  $\beta_l$  represents the difference in the log-odds between the two groups. To address the hypothesis of interest for primary hypothesis #1, we will perform a statistical test of  $H_0$ :  $\beta_l = 0$  vs.  $H_1$ :  $\beta_l \neq 0$ . Quantification of the treatment effect will be performed by exponentiation of the estimated coefficient,  $\exp(\beta_l)$ , to obtain an estimate of the odds ratio. The confidence interval will be determined similarly. The presence of a homogeneous center effect will be examined with inclusion of study center as strata using the Breslow-Day test. Generalized estimating equations to account for repeated measures within sites may be considered as well, especially in the event that significant center effects are detected. Modified Poisson regression modeling with robust standard errors will also be considered in order to estimate risk ratios for the primary outcome while adjusting for any possible covariates. While logistic regression yields odds ratios that often approximate risk ratios, direct modeling of risk ratios may yield more informative estimates of the true risk of the outcome.

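### The SAP's per-protocol analysis covers only the composite, although the protocol plans one for both primary aims. SGA, the primary safety outcome, is left without an adherence-based estimate, and for harm dilution errs towards reassurance.

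*Combined protocol and SAP*

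**What the plan says.** Protocol 4.7.1 lists SGA below the 10th percentile as the second primary outcome and names it the primary safety outcome. Protocol 5.3 describes the key analyses as "comparisons reflected by the primary and secondary aims; both intent-to-treat (as the primary) and a per-protocol approach will be used". Protocol 5.3.1, on the primary aims, compares both the composite and SGA and places per-protocol analyses among the secondary analyses.

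The SAP is narrower. Section 3.1.1 defines the primary outcome as the composite, and section 4 states: "For the primary outcome, both intent-to-treat (as the primary) and a per-protocol approach will be used". The per-protocol set defined there restricts the Lower BP arm only (more than 80% compliance and attendance at every scheduled visit) and leaves the Standard arm whole.

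For SGA, SAP 3.2.2 plans a chi-square test against a null of no difference, group rates, and a risk ratio with 95% CI: "All individuals will be analyzed as randomized to the two treatment groups, regardless of whether they adhered to their assigned treatment". Its sensitivity analyses follow the composite's plan (complete-case, best case and worst case), so they deal with missing outcomes and not with adherence. SAP 3.2.1 adds SGA below the 5th and 3rd percentiles. No margin or bound on excess SGA is stated.

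On expected noncompliance, the revised sample size (SAP 3.1.4) assumes "10% noncompliance, 10% crossover, and 85% power". Protocol 5.1.1 describes the control-arm part thus: "there will be up to a 10% rate of protocol violations (treatment in the control group without meeting criteria for severe hypertension".

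**The concern.** Dilution by nonadherence and crossover is conservative for a benefit, because it makes an effect harder to claim. For a harm it works the other way: it shrinks the observed excess and makes a finding of no difference easier to reach. SGA is the outcome on which the plan sets possible harm against benefit, and the protocol (2.6.2.1 and 2.6.2.2) cites earlier signals of increased SGA as a reason for concern. The SAP therefore omits an adherence-based look for the outcome where it is most informative, although the protocol had planned one. If the SAP is followed as written, the trial can report an upper limit for SGA harm under assignment, but none for women who follow the assigned strategy.

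**Working it through.** **Inputs**
- 2404 women, 1202 per arm: "The sample size of 2404 provides adequate power to examine SGA and key components of the primary outcome separately" (SAP 3.2.3).
- The SGA row of the power table: "SGA 10-14% 35-40 ≥85" percent, that is incidence, relative effect size and power. The direction of effect is not stated.
- Two-sided alpha 0.05: "Tests of significance will be two-sided and evaluated at the 0.05 level of significance" (SAP 3.1.2).
- 10% noncompliance and 10% crossover (SAP 3.1.4).

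**Formulas**
- Power for two proportions: Φ[(|d| − 1.96·s0)/s1], with d = p1 − p0, s0 = √(2·p̄(1−p̄)/n) and s1 = √([p0(1−p0) + p1(1−p1)]/n).
- Dilution: Standard = p0 + 0.1d; Lower = p1 − 0.1d. The difference left is 0.8d.

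**Check that this is the plan's own dilution model.** For the composite with a 25% reduction from 16%, d = −4 points. The diluted rates are 16 − 0.4 = 15.6% and 12 + 0.4 = 12.4%, as SAP 3.1.3 states. At 85% power and alpha 0.0492 the sample sizes per arm are 1356 undiluted and 2120 diluted. Then 2120/0.92 = 2304.3, rounded up to 2305. Both table entries (1356 and 2305) reproduce.

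**The plan's SGA power.** Read as a reduction with full adherence, 10% against 6.5% at 1202 per arm gives 87.7%, so the stated figure of at least 85% reproduces. Diluted to 9.65% against 6.85%, power is 70.4%. The composite's sample size allows for noncompliance. The SGA power figure reproduces at 10% incidence with a 35% effect only if it does not.

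**The harm direction, at 1202 per arm**

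| True rates | True RR | Diluted rates | ITT RR | Power, full adherence | Power, diluted |
|---|---|---|---|---|---|
| 10% vs 13.5% | 1.35 | 10.35% vs 13.15% | 1.27 | 76.0% | 56.8% |
| 10% vs 14.0% | 1.40 | 10.40% vs 13.60% | 1.31 | 85.5% | 67.5% |
| 14% vs 18.9% | 1.35 | 14.49% vs 18.41% | 1.27 | 90.0% | 73.7% |
| 14% vs 19.6% | 1.40 | 14.56% vs 19.04% | 1.31 | 95.7% | 83.6% |

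The first row in full: d = 3.5 points; 10 + 0.35 = 10.35; 13.5 − 0.35 = 13.15; 13.15/10.35 = 1.27. With s0 = 0.01314 and s1 = 0.01312, (0.028 − 1.96 × 0.01314)/0.01312 = 0.17 and Φ(0.17) ≈ 0.57.

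**What an adherence adjustment changes.** At the expected diluted rates of that row, the ITT difference is 2.80 points with standard error 1.31, so the 95% CI is 2.80 ± 1.96 × 1.31, or 0.23 to 5.37. Dividing by the between-arm difference in exposure, 0.9 − 0.1 = 0.8, gives 3.50 points (0.28 to 6.71). The reported upper limit moves from about 5.4 to about 6.7 points. The 0.8 is treated as known here; a bootstrap would also carry its sampling error.

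**Why the existing per-protocol set should not simply be copied.** Suppose it keeps 90% of the Lower arm (an assumption) and the Standard arm stays diluted. A true RR of 1.35 from 10% then appears as 13.5/10.35 = 1.30, which recovers only part of the dilution. Attendance at every visit may also depend on how long the pregnancy lasts.

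**The case against.** **The protocol already plans it.** This stands. A reader of the SAP alone might infer that no adherence-based look at SGA exists in the plan. Protocol 5.3 and 5.3.1 do plan one, and 5.3.1 also plans a logistic model with duration of therapy. The defect is a mismatch between the two documents. SAP section 4 also mentions analyses accounting for duration of therapy, but names no outcome for them.

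**SGA is not judged by a test alone.** This also stands. The risk ratio, its 95% CI, group rates and stricter cut-offs are planned, SGA is tested at the interim analysis, and the DSMB monitors safety throughout. Nothing in the documents says that a null result will be taken as proof of safety.

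**ITT is the right primary estimand.** Agreed. The trial evaluates a treatment policy (protocol 3.3), and for harm of the policy ITT is the target. The adherence-based estimate is supportive.

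**Larger dilution figures.** One might add the further 10% of controls expected to need treatment for severe hypertension. The documents do not support this: treatment from 160/105 upwards is part of the assigned Standard strategy (protocol 3.3 and 3.6), not crossover. One might also dilute the 13.9% and 19.7% SGA rates that the protocol quotes from the trial of tight against less-tight control. Those are already rates by assigned group and compare two pressure targets, so diluting them again is unsound.

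**The complier-average estimate recovers no power.** Correct. It divides the ITT difference by the difference in exposure, so its test is essentially the ITT test. It changes the size of the estimate and its upper limit, and it needs assumptions of its own.

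**Conclusion.** The point holds as a mismatch between protocol and SAP on the primary safety outcome, with a direction of bias that makes it worth correcting. Under the plan's own 10% and 10%, ITT keeps 80% of an SGA risk difference. True risk ratios of 1.35 to 1.40 appear as 1.27 to 1.31, and power to detect them at 1202 per arm falls by 12 to 19 points across 10% to 14% incidence. That is attenuation. It would go too far to say that the plan conceals harm.

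The SGA incidences, effect sizes and noncompliance rates are the plan's; reading the effect sizes as increases is an assumption made here, since the table gives no direction. It is further assumed that nonadherence is unrelated to SGA risk, and that women who do not follow their assigned strategy have the other arm's rate. With 1142 evaluable per arm (SAP 3.1.4), the first row of the table becomes 73.8% and 54.7%, so attrition does not change the conclusion.

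**What to change.** 1. Keep ITT as the primary analysis of SGA.
2. State in SAP 3.2.2 and section 4 that a supportive adherence-based analysis also covers SGA, in line with protocol 5.3 and 5.3.1.
3. Use an estimator that keeps the randomization: the complier-average risk difference, equal to the ITT risk difference divided by the between-arm difference in exposure, with a bootstrap CI. For this analysis, count as crossover only Standard-arm treatment outside the protocol's criteria, and not treatment started at or above 160/105. Define exposure in both arms before unblinding.
4. State that a non-significant chi-square for SGA is not evidence of safety, and that the safety conclusion quotes the upper 95% limits of the ITT and adherence-adjusted estimates.

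The cost is SAP wording and one extra analysis. The pill counts and reports of off-study medication are already collected (protocol 4.4.2). The adjusted interval is wider. It assumes that assignment affects SGA only through exposure, and it reduces titrated treatment to a yes/no exposure using limited adherence data. It does not restore the lost power.
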